As Chair, do you have any real or apparent protocol-specific conflict of interest between yourself and the sponsor of the research project, or its competitor or any interest in any intervention and/or method tested in the project that might compromise this research project?

Yes (provide a description of that interest in a separate letter addressed to the HIC)
 No

I assure the HIC that the principal investigator and all members of the research team are qualified by education, training, licensure and/or experience to assume participation in the conduct of this research trial. I also assure that the principal investigator has departmental support and sufficient resources to conduct this trial appropriately.

[name], MBA
Chair Name (PRINT) and Signature

Date

Department: Department of Surgery

YNHH Human Subjects Protection Administrator Assurance Statement

Required when the study is conducted solely at YNHH by YNHH health care providers.

As Human Subject Protection Administrator (HSPA) for YNHH, I certify that:

- I have read a copy of the protocol and approve it being conducted at YNHH.
- I agree to notify the IRB if I am aware of any real or apparent institutional conflict of interest.
- The principal investigator of this study is qualified to serve as P.I. and has the support of the hospital for this research project.

YNHH HSPA Name (PRINT) and Signature _____

Date _____

For HIC Use Only

Date Approved _____

Human Investigation Committee Signature _____

This protocol is valid through _____

SECTION V: RESEARCH PLAN

1. **Statement of Purpose:** State the scientific aim(s) of the study, or the hypotheses to be tested.

Primary Objectives

The primary objective of the study is to determine the effect of percutaneous ethanol ablation on:

- a) Quality of life, through the SF-36 form
- b) Thyroid-related symptoms, through the Thyroid Symptom Questionnaire (TSQ)
- c) Pain (BPI), voice (VHI) and cosmesis (POSAS)
- d) Reduction and/or elimination of size of primary thyroid microcarcinoma

Secondary Objectives

A secondary objective of the study is to confirm the safety, feasibility, and cost of treating primary papillary thyroid microcarcinoma with percutaneous ethanol ablation.

Another secondary objective of the study is the assessment of oncologic outcomes, including disease-free survival and overall survival (exploratory endpoints).

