3. **Research Plan:** Summarize the study design and research procedures using non-technical language that can be readily understood by someone outside the discipline. Be sure to distinguish between standard of care vs. research procedures when applicable, and include any flowcharts of visits specifying their individual times and lengths. Describe the setting in which the research will take place.

The purpose of this study is to evaluate a new treatment option for the management of primary papillary thyroid microcarcinoma (PTMC). Patients referred to Yale Endocrine Surgery for management of cytology-proven PTMC (PTC measuring 1 cm or less in diameter) will be offered inclusion into the study. (See page 24 for specific exclusion criteria.) After enrollment, patients will be assigned to percutaneous ethanol ablation (PEA) of the primary PTMC. Importantly, PEA will not be offered to patients outside of inclusion in the study.

After informed consent is obtained, baseline evaluation includes the following tests:

- a) Baseline ultrasound assessment to confirm size and location of PTMC
- b) Baseline laryngoscopy before initiation of treatment
- c) Baseline quality of life assessment (“SF-36”; Appendix 1)
- d) Baseline pain assessment (“Brief Pain Inventory”, BPI; Appendix 2)
- e) Baseline voice assessment (“Voice Handicap Index”, VHI; Appendix 3)
- f) Baseline symptom assessment (“Thyroid Symptom Questionnaire”, TSQ; Appendix 4)

The SF-36 is a set of easily-administered quality-of-life measures and is a validated tool to evaluate patient quality of life [40-42]. The VHI is an established tool used to assess voice after an intervention [43-45]. The BPI is a simple, well-accepted instrument for the objective assessment of pain [46-48]. The TSQ is a 12-item based questionnaire assessing specific thyroid related symptoms.

Therapy

a. Percutaneous ethanol ablation

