Patients in the PEA group will constitute the sole treatment group of the study. These patients will be scheduled for an outpatient procedure with [name] from Interventional Radiology. The volume of 99% ethanol to be injected is calculated using a standardized formula (Ethanol Volume= length × width × height × π / 6) and instilled with a 3-4 cm long 22-25-gauge needle under ultrasound-guidance after administration of local anesthesia. If the patient cannot tolerate the procedure despite adequate local anesthesia, they will be offered conscious sedation. Conscious sedation is a combination of medicines to help you relax (a sedative) and to block pain (an anesthetic) during a medical. You will probably stay awake but may not be able to speak.

It is usually safe, however, overmedication could result in respiratory depression. The patient will be monitored carefully during the entire procedure and the appropriate equipment will be employed if needed.

The procedure itself usually takes only about 60-90 minutes and the patient will be observed for 2-3 hours in the hospital before discharge home.

All patients will receive a phone call to their home 48 hours after the PEA procedure and will be assessed for pain level and voice quality (BPI and VHI).

Every patient will be scheduled for a post-procedure visit in the endocrine surgery clinic approximately 7 – 14 days after their procedure. The post-procedure clinic visit will include the following assessments:

- a) Evaluation of the wound after the intervention
- b) Follow-up ultrasound assessment
- c) Follow-up laryngoscopy after treatment
- d) Follow-up quality of life assessment (SF-36)
- e) Follow-up pain assessment (BPI)
- f) Follow-up voice assessment (VHI)
- g) Follow-up symptom assessment (TSQ)
- h) Cosmesis assessment (“Patient and Observer Scar Assessment Scale”, POSAS; Appendix 5)

During this clinic visit, a thorough evaluation will be performed of the patient's injection site. An endocrine surgeon will evaluate the injection site during this visit using POSAS, a validated tool for the evaluation of surgical scars [49-52].

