Descriptive statistics, including mean and standard deviation for continuous variables and frequency and percentage for categorical variables, will be used to summarize patient characteristics. The adverse events will be investigated in order to assess the safety of the new procedure. The primary analysis will be comparing the pre-operative TSQ score to the post-operative TSQ score. Using standard deviation of 6.38 as reported in the DEPTH (DEPression and THyroid) study [54], the sample size of 16 achieves 90% power to detect a difference of 5.65 between pre- and post-PEA with a type I error of 0.05 using a paired t-test. This effect size is equivalent to one-level difference in responses for 6 items (such as from "Much worse" to "Little worse"), or three-level differences in responses for 2 items (such as from "Much worse" to "Much better"), etc.

Similarly, a power analysis was performed for QOL. The Physical Component and Mental Component of SF-36 will be used. The standard deviations, 9.7 and 11.0 for patients with thyroid disease, respectively, were used to estimate statistical power. The sample size of 16 in each group achieves 90% power to detect a difference of 8.6 in SF-36 Physical Component summary score and 9.8 in Mental Component summary score between the PEA and thyroidectomy groups with a type I error of 0.05.

Time and motion studies and a cost analysis will also be conducted.

SECTION VI: RESEARCH INVOLVING DRUGS, BIOLOGICS, RADIOTRACERS, PLACEBOS AND DEVICES

If this section (or one of its parts, A or B) is not applicable, state N/A and delete the rest of the section.

A. DRUGS, BIOLOGICS and RADIOTRACERS

1. Identification of Drug, Biologic or Radiotracer: What is (are) the **name(s)** of the drug(s) biologic(s) or radiotracer(s) being used? Identify whether FDA approval has been granted and for what indication(s).

Percutaneous ethanol injection is approved by the FDA and is a well-accepted treatment modality for the management of metastatic thyroid carcinoma to the neck, as well as benign thyroid cysts or autonomic nodules [27, 28, 30-32, 36, 55]. The injection of ethanol has been also used successfully in the cure of liver tumors [56-61].

1. Hay, I.D. and J.W. Charboneau, The coming of age of ultrasound-guided percutaneous ethanol ablation of selected neck nodal metastases in well-differentiated thyroid carcinoma. *J Clin Endocrinol Metab*, 2011. 96(9): p. 2717-20.

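### The SF-36 power statement is for a PEA-versus-thyroidectomy comparison that this single-arm trial cannot make, and 16 per group would give about 68% power for it, not 90%

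*Combined protocol and SAP*

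**What the plan says.** Section V, item 3 (Research Plan) describes one arm. On allocation it says "After enrollment, patients will be assigned to percutaneous ethanol ablation (PEA) of the primary PTMC", and under Therapy "Patients in the PEA group will constitute the sole treatment group of the study". Section VII, item 1 sets enrollment at 40 and gives no division into groups.

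Section V, item 1 lists "Quality of life, through the SF-36 form" as objective (a) of the primary objectives. Section V, item 12 names the TSQ at 12 months as the primary endpoint and mentions SF-36 as an additional assessment.

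Item 12 then gives two power statements. For the TSQ, using a paired t-test and an SD of 6.38: "the sample size of 16 achieves 90% power to detect a difference of 5.65 between pre- and post-PEA". The next paragraph presents the SF-36 calculation as analogous. On the SDs it says "The standard deviations, 9.7 and 11.0 for patients with thyroid disease, respectively, were used to estimate statistical power", and on power "The sample size of 16 in each group achieves 90% power to detect a difference of 8.6 in SF-36 Physical Component summary score", continuing with "9.8 in Mental Component summary score between the PEA and thyroidectomy groups with a type I error of 0.05".

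**The concern.** The SF-36 sentence powers a contrast between two groups, and only one of them exists. Within the study's own care, thyroidectomy arises only for patients whose disease progresses (Section V, items 3, 9 and 10). Item 12 expects no progression related to the procedure within a feasible follow-up, so those patients cannot supply a comparison group of 16. No historical or external control is described.

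The number looks wrong as well. The SF-36 differences are almost the same multiple of their SDs as the TSQ difference is of its SD, and the same 16 and 90% are quoted. Sixteen patients in a paired test and 16 per group in a two-sample test cannot both give 90% at the same standardized difference.

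At stake is what the trial can be said to show on an outcome listed among its primary objectives. A reader of item 12 would conclude that the trial has 90% power to show a quality-of-life difference from surgery. It cannot test that difference at all. For the pre/post SF-36 comparison that it can make, the plan names no test and gives no power figure.

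**Working it through.** **Inputs (Section V, item 12).** PCS difference 8.6, SD 9.7. MCS difference 9.8, SD 11.0. TSQ difference 5.65, SD 6.38. n = 16 (SF-36: 16 in each of two groups). Type I error 0.05. The SF-36 sentence does not say whether the test is one- or two-sided; two-sided is assumed and one-sided is shown as a variant.

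**Standardized differences.**
- PCS: 8.6 / 9.7 = 0.887
- MCS: 9.8 / 11.0 = 0.891
- TSQ: 5.65 / 6.38 = 0.886

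**Step 1. The TSQ figure reproduces.** For a paired t-test, the noncentrality is d × √n on n − 1 = 15 df. For the TSQ this is 0.886 × 4 = 3.54, which gives 91.1% power. The stated 90% is confirmed.

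**Step 2. The SF-36 figure as worded does not.** For two independent groups, the noncentrality is d × √(n/2) on 2n − 2 = 30 df:
- PCS: 0.887 × √8 = 2.51, power 68.0%
- MCS: 0.891 × √8 = 2.52, power 68.4%

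**Step 3. More lenient two-group readings.**

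| Reading | PCS | MCS |
|---|---|---|
| 16 per group, two-sided t | 68.0% | 68.4% |
| 16 per group, two-sided normal approximation | 70.8% | 71.2% |
| 16 per group, one-sided t | 79.0% | 79.3% |
| 16 per group, one-sided normal approximation | 80.6% | 80.9% |
| 20 per group (all 40 patients), two-sided t | 78.0% | 78.4% |
| 16 versus 24, two-sided t | 76.3% | 76.7% |

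None is near 90%. A baseline-adjusted two-group analysis would reach it only with a baseline-to-follow-up correlation between 0.6 and 0.7 (PCS: 85.8% at 0.6, 92.5% at 0.7). The protocol describes no such analysis.

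**Step 4. What two groups would need.** At these differences, 90% power (two-sided t) requires 28 per group. With 16 per group, the difference detectable at 90% power is 1.185 SD: 1.185 × 9.7 = 11.5 (PCS) and 1.185 × 11.0 = 13.0 (MCS).

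**Step 5. The calculation that fits.** As a paired t-test with n = 16, taking 9.7 and 11.0 as SDs of the change:
- PCS: 0.887 × 4 = 3.55, power 91.2%
- MCS: 0.891 × 4 = 3.56, power 91.4%

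With n = 15 the values are 89.1% and 89.4%, so 16 is the smallest number reaching 90%.

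**Step 6. How far Step 5 depends on the SD.** If 9.7 and 11.0 are cross-sectional SDs, the SD of change is SD × √(2(1 − r)), where r is the pre/post correlation. The protocol gives no r, so a range is assumed:

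| Assumed r | SD of change, PCS / MCS | Power at n = 16, PCS / MCS | Detectable at 90%, n = 16, PCS / MCS | Detectable at 90%, n = 40, PCS / MCS |
|---|---|---|---|---|
| 0 | 13.7 / 15.6 | 65% / 65% | 11.9 / 13.5 | 7.2 / 8.2 |
| 0.3 | 11.5 / 13.0 | 80% / 80% | 10.0 / 11.3 | 6.0 / 6.8 |
| 0.5 | 9.7 / 11.0 | 91% / 91% | 8.4 / 9.5 | 5.1 / 5.8 |
| 0.7 | 7.5 / 8.5 | 99% / 99% | 6.5 / 7.4 | 4.0 / 4.5 |

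Using the quoted SDs directly as SDs of change is the same as assuming r = 0.5.

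**The case against.** The best defense is that this is leftover wording around a sound calculation. The SF-36 paragraph follows the TSQ paired test and is presented as parallel to it, the standardized differences nearly coincide, and 16 is exactly the smallest n that reaches 90% in a paired test. On that reading, 68%, 28 per group and 11.5/13.0 points describe an analysis nobody intends to run and are not a shortfall in this trial's power. This largely stands as an account of how the sentence arose. It does not rescue the sentence, which names two groups and a comparator in plain terms.

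It can also be said that SF-36 is not the primary endpoint: item 12 names the TSQ, whose power statement holds, and nothing in recruitment, treatment or follow-up depends on the SF-36 sentence. That is true and limits the consequences. SF-36 is still the first-listed primary objective, and a power claim made for it should be one the design can support.

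Finally, the replacement figures rest on an unverified SD. The protocol describes 9.7 and 11.0 only as values for patients with thyroid disease, which may well mean cross-sectional SDs. This stands, and it is why the restated sentence has to declare its assumption. Likewise, the figures for 40 patients assume that all 40 are evaluable.

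**Conclusion.** The concern holds on both counts. The SF-36 power sentence describes a comparison for which the trial has no second group. For that comparison, 16 per group would give 68.0% (PCS) and 68.4% (MCS) power with a two-sided test at 0.05, or about 79% one-sided, against the stated 90%. The figures are consistent with a paired pre/post test in 16 patients (91.2% and 91.4%), but only if the quoted SDs are SDs of change. If they are cross-sectional, PCS power at n = 16 runs from 65% to 99% for assumed correlations of 0 to 0.7. The TSQ power statement and the trial's size are not affected.

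**What to change.** In Section V, item 12, remove the two-group wording and the phrase "between the PEA and thyroidectomy groups with a type I error of 0.05", and restate the SF-36 calculation as a paired t-test on the pre-/post-PEA change. The new text should give:

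- the visit compared with baseline;
- the sidedness of the test;
- the number of evaluable patients assumed;
- the assumed SD of change, with its source or the pre/post correlation behind it, and the range of power if that correlation is uncertain.

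With SDs of change of 9.7 and 11.0, two-sided 0.05 and 90% power, the detectable changes are about 8.4 (PCS) and 9.5 (MCS) points with 16 evaluable patients, and about 5.1 and 5.8 with 40. Add a sentence saying that the trial will draw no comparative conclusion against thyroidectomy.

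The cost is a few lines of protocol wording, with no added patients, visits or procedures. The only thing given up is a comparative claim that the design cannot support.

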- a. What is the Investigational New Drug (IND) **number** assigned by the FDA?
- b. Who holds the IND?
- c. All protocols which utilize a radiotracer not approved by, but regulated by the FDA must provide the IND number: _____

Alternatively, use of the investigational radiotracer may be under RDRC/RSC oversight: (check if appropriate) _____

For all investigational radiotracers, attach a copy of the RDRC/RSC application (for radioisotopes used in the PET Center, PET Center personnel may complete this step)

Go to <http://rsc.med.yale.edu/login.asp?url=myApps.asp>. When you have logged in, complete the application and attach a copy to this submission. NOT APPLICABLE

Alternatively, an **exemption from IND filing requirements** may be sought for a clinical investigation of a drug product that is lawfully marketed in the United States. If there is no IND and an exemption is being sought, review the following categories and complete the category that applies (*and delete the inapplicable categories*): NOT APPLICABLE

2. **Background Information:** Provide a description of previous human use, known risks, and data addressing dosage(s), interval(s), route(s) of administration, and any other factors that might influence risks. If this is the first time this drug is being administered to humans, include relevant data on animal models.

Percutaneous ethanol injection is approved by the FDA and is a well-accepted treatment modality for the management of metastatic thyroid cancer in the neck, as well as benign thyroid cysts or nodules. Ethanol (99%) is injected through the skin into the thyroid tissue under ultrasound guidance and it has been reported in the literature that 0.1 to 1.0 cc ethanol is sufficient for the successful ablation of a PTMC [27, 28, 30-32, 36, 55]. The actual volume of ethanol to be instilled into a particular tumor will be calculated through a standard formula (Ethanol Volume= length × width × height × π / 6). Based on our experience and the existing literature, we believe that most PTMCs will be completely treated with a single procedure, given the small size of the tumors (≤ 1 cm). However, if follow-up ultrasound demonstrates residual tumor after initial treatment, re-treatment will be permitted.

1. Howlader, N.N., AM, *SEER cancer Statistics Review*. 2013.
2. Pacini, F., *Management of papillary thyroid microcarcinoma: primum non nocere!* J Clin Endocrinol Metab, 2013. 98(4): p. 1391-3.

- d. Describe the procedures that are in place to safeguard participants receiving placebo.

6. **Use of Controlled Substances:**

Will this research project involve the use of controlled substances in human subjects?

Yes No *See HIC Application Instructions to view controlled substance listings.*

If yes, is the use of the controlled substance considered:

Therapeutic: The use of the controlled substance, within the context of the research, has the potential to benefit the research participant.

Non-Therapeutic: *Note, the use of a controlled substance in a non-therapeutic research study involving human subjects may require that the investigator obtain a Laboratory Research License. Examples include controlled substances used for basic imaging, observation or biochemical studies or other non-therapeutic purposes. See Instructions for further information.*

7. **Continuation of Drug Therapy After Study Closure** Not applicable to this project

Are subjects provided the opportunity to continue to receive the study drug(s) after the study has ended?

Yes If yes, describe the conditions under which continued access to study drug(s) may apply as well as conditions for termination of such access.

No If no, explain why this is acceptable.

B. DEVICES

1. Are there any investigational devices used or investigational procedures performed at YNHH, e.g., YNHH Operating Room or YNHH Heart and Vascular Center? Yes No
If Yes, please be aware of the following requirements:

- a. A YNHH New Product/Trial Request Form must be completed;
- b. Your request must be reviewed and approved by a Hospital Committee before patients may be scheduled; and
- c. The notice of approval from YNHH must be submitted to the HIC for the protocol file.

Please contact [name], [contact] or [contact], to initiate the process.

2. What is the name of the device to be studied in this protocol?

Has this device been FDA approved? Yes No

If yes, state for what indication.

3. **Background Information:** Provide a description of previous human use, known risks, and any other factors that might influence risks. If this is the first time this device is being used in humans, include relevant data on animal models.

4. **Source:**

a) Identify the source of the device to be used.

b) Is the device provided free of charge to subjects? Yes No

5. What is the PI's assessment of risk level (significant or non-significant) associated with the use of the device?

Significant Risk (SR) Device Study: A study of a device that presents a potential for serious risk to the health, safety, or welfare of a participant and 1) is intended as an implant; 2) is used in supporting or sustaining human life; or otherwise prevents impairment of human health; 3) is of substantial importance in diagnosing, curing, mitigating or treating disease, or otherwise prevents

impairment of human health; or 4) otherwise presents a potential for serious risk to the health, safety, or welfare of a participant.

Significant Risk Devices require an Investigational Device Exemption (IDE) issued by the FDA.

What is the **IDE number** assigned by the FDA?

Did the FDA approve this IDE as **Category A** (experimental/investigational) or as **Category B** (non-experimental/investigational)?

Who holds the IDE?

Non-Significant Risk (NSR) Device Study: A study of a device that does not meet the definition for a significant risk device and does not present a potential for serious risk to the health, safety, or welfare of participants. Note that if the HIC concurs with this determination, an IDE is not required.

6. Abbreviated IDE or Exempt IDE: There are abbreviated requirements for an IDE and there also are exemptions to the requirement for an IDE. *See the criteria in the HIC Application Instructions, Section VI.B.4 at http://www.yale.edu/hrpp/resources/docs/100FR1aHICProtocol_Application_Instructions5-25-11.pdf to determine if these pertain to this study.*

Abbreviated IDE or Exempt IDE – *If criteria set forth in the HIC Application Instructions are met, copy and paste the completed relevant section from the Instructions into this application.*

7. Investigational device accountability:

State how the PI, or named designee, ensures that an investigational device is used only in accordance with the research protocol approved by the HIC, and maintains control of the investigational device as follows:

Maintains appropriate records, including receipt of shipment, inventory at the site, dispensation or use by each participant, and final disposition and/or the return of the investigational device (or other disposal if applicable):

Documents pertinent information assigned to the investigational device (e.g., date, quantity, batch or serial number, expiration date if applicable, and unique code number):

Stores the investigational device according to the manufacturer's recommendations with respect to temperature, humidity, lighting, and other environmental considerations:

Ensures that the device is stored in a secure area with limited access in accordance with applicable regulatory requirements:

Distributes the investigational device to subjects enrolled in the IRB-approved protocol:

SECTION VII: RECRUITMENT/CONSENT AND ASSENT PROCEDURES**1. Targeted Enrollment: Give the number of subjects:**

- a. Targeted for enrollment at Yale for this protocol: 40
- b. If this is a multi-site study, give the total number of subjects targeted across all sites
N/A

2. Indicate recruitment methods below. Attach copies of any recruitment materials that will be used.

 Flyers	 Internet/Web Postings	 Radio
 Posters	 Mass E-mail Solicitation	 Telephone
 Letter	 Departmental/Center Website	 Television
 Medical Record Review	 Departmental/Center Research Boards	 Newspaper
 Departmental/Center Newsletters	 Web-Based Clinical Trial Registries	
 YCCI Recruitment database	 Clinicaltrials.gov Registry (do not send materials to HIC)	
 Other (describe): Patients who meet eligibility criteria will be approached by an attending surgeon at Yale Endocrine Surgery and will be asked about their interest in enrollment into the study.		

3. Recruitment Procedures:

- a. Describe how potential subjects will be identified.

A letter will be sent to referring endocrinologists to raise awareness for this clinical trial. This letter will inform the endocrinologists about the general study purpose, study design, and potential inclusion and exclusion criteria. All potential patients will be referred to Yale Endocrine Surgery for final assessment of eligibility. We include a copy of this letter with the amendment form.

All patients referred to Yale Endocrine Surgery who meet eligibility criteria and do not meet exclusion criteria will be offered enrollment in the study. The attending endocrine surgeon (Drs. [name], [name], [name] or [name]) will determine eligibility at the time of the initial clinic visit.

- b. Describe how potential subjects are contacted.

Potential subjects will be approached during their regularly scheduled Yale Endocrine Surgery clinic appointment.

- c. Who is recruiting potential subjects?

Attending endocrine surgeons at Yale Endocrine Surgery will approach patients to discuss their interest in enrollment. Referring physicians who have heard about the study may also refer patients specifically for a discussion of enrollment into the study. Patients who have heard about the study may self-refer for a discussion of enrollment into the study.

4. Screening Procedures

- a. Will email or telephone correspondence be used to screen potential subjects for eligibility prior to the potential subject coming to the research office? Yes No

b. If yes, identify below all health information to be collected as part of screening and check off any of the following HIPAA identifiers to be collected and retained by the research team during this screening process. N/A

5. Assessment of Current Health Provider Relationship for HIPAA Consideration:

Does the Investigator or any member of the research team have a direct existing clinical relationship with any potential subject?

Yes, all subjects
 Yes, some of the subjects
 No

If yes, describe the nature of this relationship.

All patients, who are enrolled in this study, will have clinical relationship with the principle investigator, as they will undergo surveillance for their procedure for 5 years. They will be scheduled for follow up clinic visits, initially by the surgical team (first clinic visit after procedure) and afterwards by [name] (also included in protocol; member of study team). For details of follow up clinic visits please see Appendix 6.

6. Request for waiver of HIPAA authorization: (When requesting a waiver of HIPAA Authorization for either the entire study, or for recruitment purposes only. Note: if you are collecting PHI as part of a phone or email screen, you must request a HIPAA waiver for recruitment purposes.)

N/A

Choose one: For entire study: _____ For recruitment purposes only: _____

- i. Describe why it would be impracticable to obtain the subject's authorization for use/disclosure of this data;
- ii. If requesting a waiver of **signed** authorization, describe why it would be impracticable to obtain the subject's signed authorization for use/disclosure of this data;

By signing this protocol application, the investigator assures that the protected health information for which a Waiver of Authorization has been requested will not be reused or disclosed to any person or entity other than those listed in this application, except as required by law, for authorized oversight of this research study, or as specifically approved for use in another study by an IRB.

Researchers are reminded that unauthorized disclosures of PHI to individuals outside of the Yale HIPAA-Covered entity must be accounted for in the "accounting for disclosures log", by subject name, purpose, date, recipients, and a description of information provided. Logs are to be forwarded to the Deputy HIPAA Privacy Officer.

7. Required HIPAA Authorization: If the research involves the creation, use or disclosure of protected health information (PHI), separate subject authorization is required under the HIPAA Privacy Rule. Indicate which of the following forms are being provided:

- Compound Consent and Authorization form
- HIPAA Research Authorization Form

N/A

8. Consent Personnel: List the names of all members of the research team who will be obtaining consent/assent.

- a. [name]
- b. [name], MBA
- c. [name], PhD
- d. [name]
- e. [name]
- f. [name]
- g. [name], MS
- h. [name], PhD
- i. [name], MBA

9. Process of Consent/Accent: Describe the setting and conditions under which consent/assent will be obtained, including parental permission or surrogate permission and the steps taken to ensure subjects' independent decision-making.

Patients will be consented in the Yale Endocrine Surgery clinic during their evaluation. This study does not involve children or patients without decision-making capacity.

10. Evaluation of Subject(s) Capacity to Provide Informed Consent/Accent: Indicate how the personnel obtaining consent will assess the potential subject's ability and capacity to consent to the research being proposed.

The patient will be assessed by a physician before obtaining informed consent/ assent. It is the duty of the physician to use his/her clinical judgment to determine if the patient has the ability and capacity to make his or her decision regarding medical treatment. In some circumstances, the patient may lack the mental capability to consent for the planned procedure. Circumstances such as being under the influence of drugs or alcohol may constitute grounds that the patient is temporarily incompetent to consent and the patient will not be consented for the planned procedure. Patients suffering from dementia are also considered incompetent to consent and the study team will exclude the patients from the study.

In the absence of any concerns about the patient's ability to consent, the patient will be asked to sign the consent for the procedure.

11. Documentation of Consent/Accent: Specify the documents that will be used during the consent/assent process. Copies of all documents should be appended to the protocol, in the same format that they will be given to subjects.

We include our "Adult Informed Consent Form". We do not plan to enroll patients into the study who are decisionally impaired or minors that would require assent forms or child assent forms, respectively.

12. Non-English Speaking Subjects: Explain provisions in place to ensure comprehension for research involving non-English speaking subjects. Translated copies of all consent materials must be submitted for approval prior to use.

We will not include non-English speaking subjects for this study.

13. Consent Waiver: In certain circumstances, the HIC may grant a waiver of signed consent, or a full waiver of consent, depending on the study. If you will request either a waiver of consent, or a waiver of signed consent for this study, complete the appropriate section below.

- Not requesting a consent waiver
- Requesting a waiver of signed consent
- Requesting a full waiver of consent

A. Waiver of signed consent: (Verbal consent from subjects will be obtained. **If PHI is collected, information in this section must match Section VII, Question 6**)

- Requesting a waiver of signed consent for Recruitment/Screening only

If requesting a waiver of signed consent, please address the following:

a. Would the signed consent form be the only record linking the subject and the research?

- Yes
- No

b. Does a breach of confidentiality constitute the principal risk to subjects?

- Yes
- No

OR

c. Does the research activity pose greater than minimal risk?

- Yes **If you answered yes, stop. A waiver cannot be granted.** Please note:

Recruitment/screening is generally a minimal risk research activity

- No

AND

d. Does the research include any activities that would require signed consent in a non-research context? Yes No

- Requesting a waiver of signed consent for the Entire Study (Note that an information sheet may be required.)

If requesting a waiver of signed consent, please address the following:

a. Would the signed consent form be the only record linking the subject and the research?
 Yes No

b. Does a breach of confidentiality constitute the principal risk to subjects?
 Yes No

OR

c. Does the research pose greater than minimal risk? Yes *If you answered yes, stop. A waiver cannot be granted.* No
AND

d. Does the research include any activities that would require signed consent in a non-research context? Yes No

B. Full waiver of consent: (No consent from subjects will be obtained for the activity.)

Requesting a waiver of consent for Recruitment/Screening only

a. Does the research activity pose greater than minimal risk to subjects?
 Yes *If you answered yes, stop. A waiver cannot be granted.* Please note: Recruitment/screening is generally a minimal risk research activity
 No

b. Will the waiver adversely affect subjects' rights and welfare? Yes No

c. Why would the research be impracticable to conduct without the waiver?

d. Where appropriate, how will pertinent information be returned to, or shared with subjects at a later date?

Requesting a full waiver of consent for the Entire Study (Note: If PHI is collected, information here must match Section VII, question 6.)

If requesting a full waiver of consent, please address the following:

a. Does the research pose greater than minimal risk to subjects?
 Yes *If you answered yes, stop. A waiver cannot be granted.*
 No

b. Will the waiver adversely affect subjects' rights and welfare? Yes No

c. Why would the research be impracticable to conduct without the waiver?

d. Where appropriate, how will pertinent information be returned to, or shared with subjects at a later date?

SECTION VIII: PROTECTION OF RESEARCH SUBJECTS

Confidentiality & Security of Data:

a. What protected health information (medical information along with the HIPAA identifiers) about subjects will be collected and used for the research?
 We will collect sufficient information about each enrollee such that should they move away from Yale-New Haven or they become otherwise "lost-to-follow-up", we can continue to track them using state and nationally-available resources such as the National Death Index,

Social Security Death Index and the Connecticut Tumor Registry. To ensure this, we will be collecting the following PHI on each enrollee:

- 1) Full given and surname
- 2) Location (city and state) and date of birth
- 3) Social Security Number
- 4) Current residential address and best contact phone number
- 5) Medical record number for Yale New Haven Hospital

b. How will the research data be collected, recorded and stored?

Data will be collected from both direct patient interview and extraction from the medical record. These data will be input into the OnCore clinical trials management system directly from the medical record. Patient surveys, which are completed in paper format, will be stored in a single, locked file cabinet and kept separate from all the remaining study documents; these data will be input into the OnCore clinical trials management system. An electronic database will be created from the data contained in OnCore. This database will serve as a standalone product to allow us to track participants and samples. It will be stored on the limited-access Yale secure server. The data in OnCore will be kept indefinitely; the research database will be de-identified one year after the end of the study and the data kept in this anonymous form indefinitely on the secure server.

c. How will the digital data be stored? CD DVD Flash Drive Portable Hard Drive Secured Server Laptop Computer Desktop Computer Other

d. What methods and procedures will be used to safeguard the confidentiality and security of the identifiable study data and the storage media indicated above during and after the subject's participation in the study?

Do all portable devices contain encryption software? Yes No

If no, see <http://hipaa.yale.edu/guidance/policy.html>

